### 2.9.8. Other Statistical Considerations

In addition to the estimation of the bias-adjusted variance of the log-transformed 24-hour UPE change from baseline to Week 36 in the SSRE (Section 1.3.3), the bias-adjusted variance of the log-transformed 24-hour uPCR change from baseline to Week 36 will be estimated in a blinded fashion using the same formula in Section 1.3.3. If the log-transformed 24-hour uPCR bias-adjusted variance is substantially smaller than the log-transformed 24-hour UPE bias-adjusted variance, the primary endpoint may be changed to log-transformed 24-hour uPCR at Week 36 after consultation with the US Food and Drug Administration.

## 3. STATISTICAL SUMMARIES

### 3.1. General Conventions

All statistical analyses will be performed using SAS version 9.4 or later (SAS Institute Inc., Cary, NC). Study endpoints will be summarized with descriptive statistics, which include n, mean, standard deviation, median, and range (minimum, maximum) for continuous variables, and frequencies and percentages for categorical variables. All statistical tests will be performed at the two-sided significance using the applicable alpha level. Confidence intervals will be similarly constructed two-sided at the applicable confidence level.

## 3.2. Patient Disposition and Treatment

### 3.2.1. Patient Disposition

Data will be displayed in both the high-risk proteinuria group (baseline UPE  $\geq 2$  g/day) and the all-patients population (baseline UPE  $> 1$  g/day).

An accounting of study patients by disposition will be tabulated by treatment group for the randomized population. The number of patients in each analysis population will be summarized by treatment group. Patients who discontinued study drug prematurely or withdrew from the study will be summarized and listed with reason for early termination/withdrawal. Patients who re-initiated study treatment will be summarized by treatment group.

Furthermore, the number of patients who receive open-label treatment with narsoplimab will be summarized by treatment group for the FAS population. Time from randomization to the date of the first dose of open-label narsoplimab will be analyzed by the KM method for each treatment group for the FAS population. Patients who have not received open-label narsoplimab-treatment will be censored at the last known date on study. Median time with 95% CI will be provided by treatment group.

### 3.2.2. Study Treatment Compliance and Extent of Exposure

#### 3.2.2.1. Study Treatment Compliance

Because all dosing will be under direct supervision of study personnel, treatment compliance will not be analyzed. Dosing information will be summarized and listed by treatment group in both the high-risk proteinuria group (baseline UPE  $\geq 2$  g/day) and the all-patients population (baseline UPE  $> 1$  g/day).

#### 3.2.2.2. Extent of Study Drug Exposure

The following exposure items will be summarized with descriptive statistics by treatment group for the safety analysis set:

- Cumulative study drug doses in milligrams taken by blinded treatment period (the Initial Treatment Period, the extended treatment period, the retreatment period, and the entire blinded treatment period) and treatment group
- Cumulative narsoplimab doses in milligrams during the open-label treatment period by treatment group
- Duration of treatment in weeks by blinded treatment period, which is defined as (the last dose date of the treatment period – the first dose date of the treatment period + 7)/7
- Duration of open-label treatment period in weeks
- Absolute dose intensity (ADI), which is defined as the actual dose taken in milligrams per week by blinded treatment period. (ADI = Cumulative doses taken in milligrams /Duration of blinded treatment in weeks)

- Relative dose intensity (RDI), which is defined as the ADI as a percentage of the intended dose intensity (IDI) by blinded treatment period,  $RDI = ADI/IDI \times 100$ , where  $IDI = 370 \text{ mg/week}$

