9.2. Vehicle Control to Match Narsoplimab

Vehicle control, 50 mL solution, for patients randomized to the control arm, will be commercially packaged 5% dextrose in water (D5W) or normal saline solution.

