14.1.12. Safety Analyses

14.1.12.1. Extent of Exposure

The following exposure items will be summarized with descriptive statistics by treatment group for the safety analysis set:

- Cumulative doses in milligrams taken by blinded treatment period (the Initial Treatment Period, the extended treatment period, the retreatment period, and the entire treatment period)
- Cumulative narsoplimab doses in milligrams during the open-label treatment period for the placebo group
- Duration of treatment in weeks by blinded treatment period, which is defined as (the last dose date of the treatment period – the first dose date of the treatment period + 7)/7
- Duration of open-label treatment period in weeks
- Absolute dose intensity (ADI), which is defined as the actual dose taken in milligrams per week by blinded treatment period. (ADI = Cumulative doses taken in milligrams /Duration of blinded treatment in weeks)
- Relative dose intensity (RDI), which is defined as the ADI as a percentage of the intended dose intensity (IDI) by blinded treatment period, RDI = ADI/IDI × 100, where IDI = 370 mg/week.

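### Relative dose intensity over the entire blinded period counts planned off-treatment months, so a retreated patient who received every infusion scores about 29% to 80%

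*SAP*

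**What the plan says.** SAP 3.2.2.2 (Extent of Study Drug Exposure) summarizes exposure by blinded treatment period. Its list names the initial period and then "the extended treatment period, the retreatment period, and the entire blinded treatment period". The duration item begins "Duration of treatment in weeks by blinded treatment period, which is defined as (the last dose date of the treatment period", and its formula in full is "the last dose date of the treatment period – the first dose date of the treatment period + 7)/7". Absolute dose intensity follows as "ADI = Cumulative doses taken in milligrams /Duration of blinded treatment in weeks". Relative dose intensity compares that rate with a constant: "RDI = ADI/IDI × 100, where IDI = 370 mg/week" (Protocol 14.1.12.1, which uses the same definitions). Neither document takes off-drug intervals out of the denominator, and neither counts infusions that were planned but not given.

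The design plans such intervals (Protocol 7.1, Table 1 and 10.2.7). Everyone is due 12 weekly infusions. Six more follow only if 24-hour UPE exceeds 1 g at Week 12. After that, study drug is given only on relapse: 6 infusions after Week 24, 30 or 36, and 12 after Week 48 or 72, each course at most once.

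On the control arm, Protocol 9.2 says the vehicle "will be commercially packaged 5% dextrose in water (D5W) or normal saline solution".

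**The concern.** RDI should say how much of the intended drug was given. Between courses the plan intends no drug, but the formula treats those weeks as weeks in which 370 mg was due. The entire-period figure then mixes adherence with the timing of relapse: two patients with the same infusions and perfect attendance get different scores because one relapsed later. Relapse is defined on proteinuria, so the exposure measure becomes partly a readout of an efficacy outcome.

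A second weakness runs the other way and applies to every period. Duration ends at the last infusion actually given, so infusions missed at the end of a course never reach the denominator.

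What is at stake is the reading of the exposure tables. A low entire-period RDI could be taken as poor dosing when none occurred, and a high one could include patients who stopped early.

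**Working it through.** **Inputs.** Duration, ADI, RDI and 370 mg/week from SAP 3.2.2.2. Course lengths of 12, 6, 6 and 12 weekly infusions from Protocol 7.1. Target days from SAP Table 2: Week 24 = Day 162, Week 48 = Day 330, Week 72 = Day 498. Extended treatment starts within 14 days of the twelfth infusion (Protocol 10.2.4), so Day 85 to Day 92. The first retreatment infusion is due within 7 days of receiving the UPE result (Protocol 10.2.7.1 and 10.2.7.2). Laboratory turnaround is not given, so total lags of 7, 14 and 21 days after the assessment target day are **assumed**.

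**Formula.** With every infusion at 370 mg, RDI = 100 × infusions / weeks, where weeks = (last dose day − first dose day + 7)/7.

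**The plan's own reference value.** Twelve weekly infusions, Day 1 to Day 78: (78 − 1 + 7)/7 = 12 weeks; 12 × 370 / 12 = 370 mg/week; RDI 100%. The formula works for one uninterrupted course.

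**Entire blinded period, every planned infusion given, 7-day lag:**

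| Courses received | Infusions | Last dose day | Weeks | RDI |
|---|---|---|---|---|
| Initial + extended (ExT1 Day 85) | 18 | 120 | 18 | 100% |
| Initial + extended (ExT1 Day 92) | 18 | 127 | 19 | 94.7% |
| Initial + extended + 6-week after Week 24 | 24 | 204 | 30 | 80.0% |
| Initial + 12-week after Week 48 | 24 | 414 | 60 | 40.0% |
| Initial + 12-week after Week 72 | 24 | 582 | 84 | 28.6% |
| All four courses, last after Week 72 | 36 | 582 | 84 | 42.9% |

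Over all combinations with at least one retreatment, the range is 28.6% to 80.0%. The two rows with initial plus 12-week retreatment show the timing effect: the same 24 infusions score 40.0% or 28.6% depending only on when relapse was found.

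**Sensitivity to lag.** The 24/60 case becomes 24/61 = 39.3% at 14 days and 24/62 = 38.7% at 21 days. The four-course case at 14 days is 36/85 = 42.4%. At 21 days the range is 24/86 = 27.9% to 24/32 = 75.0%.

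**Retreatment row, if both courses are pooled** (18 infusions): 18/60 = 30.0% (Weeks 24 and 72) to 18/24 = 75.0% (Weeks 36 and 48). Computed per course, each gives 100%.

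**Early stop.** Infusions on Days 1, 8 and 15: (15 − 1 + 7)/7 = 3 weeks; 3/3 = 100%, in both the initial and the entire period.

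**With the fix.** Summed course durations give 24/(12 + 12) = 100% and 36/(12 + 6 + 6 + 12) = 100%. The early stopper's RDI remains 100%, so a count is also needed: 3/12 = 25%. A count alone would lose delays: 12 infusions spread over 14 weeks give 12/14 = 86% as a weekly rate, but 12/12 = 100% as a count.

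**The case against.** The best case for leaving the text alone is that the affected rows are few and nothing inferential rests on them. Initial and extended RDI are reported separately and contain no planned gap. The gap error needs at least one relapse retreatment, and no document says how many patients will have one, so the effect on a tabulated mean or median is unknown. The retreatment period is not defined in the SAP; the protocol describes a 6-week and a 12-week retreatment period separately, and the 30% to 75% range applies only if they are pooled. All of this stands and limits the point.

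A reader might infer more than the documents support:

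- **That early stopping would go unseen, or that RDI is the only dosing measure.** SAP 3.2.1 summarizes and lists premature discontinuations with reasons, SAP 3.2.2.1 summarizes and lists dosing information, and SAP 3.2.2.2 reports cumulative mg and duration. The 3-infusion patient appears there as 1,110 mg over 3 weeks, against 4,440 mg over 12 for a full initial course. The Per-Protocol set in SAP 2.2 also requires at least 10 initial infusions. Only the ratio hides the stop.
- **That durable response in general looks like poor dosing.** A fully dosed responder who never relapses scores about 95% to 100%. The inverse relation holds only among retreated patients.
- **That RDI is undefined on placebo.** With 0 mg and a positive duration it is 0: uninformative, but computable.

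The objection does not remove the entire-period fault. Both documents request that figure, and the stated rule gives a misleading one for any retreated patient.

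**Conclusion.** The point holds in limited form. For the entire blinded period, and for the retreatment period if its courses are pooled, first-to-last-dose time includes planned off-drug months while intended intensity stays at 370 mg/week. A fully dosed, retreated patient scores about 29% to 80% under a 7-day lag from assessment to first retreatment infusion, and slightly less under longer lags. Separately, RDI in any period stays at 100% after an early stop, although neighbouring outputs reveal it.

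The individual scores rest on the stated formula, SAP Table 2 target days, full attendance and the assumed lags. How far group summaries would shift cannot be determined from the documents. No endpoint, analysis set, test or error rate uses ADI or RDI, so the consequence is confined to descriptive exposure reporting. The point concerns the exposure measure only, not the dosing schedule.

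**What to change.** In SAP 3.2.2.2 and Protocol 14.1.12.1:

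1. For the entire blinded period and any pooled retreatment period, define duration as the sum of the individual course durations (initial, extended, 6-week, 12-week), so that planned off-drug intervals drop out. Keep the existing formula within a course, so that delays still lower the rate.
2. Count a COVID-19 re-initiation as a new course. Otherwise the interruption enters the denominator, including that of the initial-period row. State whether infusions not given in the abandoned course remain in the planned count.
3. State whether the retreatment row pools the 6-week and 12-week courses.
4. Add a line, by course and for both arms, of infusions received over infusions planned (12, 6, 6 or 12). This shows early stopping and gives placebo a usable measure in place of 0 mg.

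The cost is revised wording in two sections, slightly more derivation work and one extra table line. No new data are needed and no clinical rule changes.

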### **3.2.3. Demographics and Baseline Characteristics**

Demographic and other baseline characteristics will be listed and summarized by treatment group in both the high-risk proteinuria group and the all-patients population.

### **3.2.4. Concomitant Medications**

Concomitant medications will be coded with World Health Organization (WHO) Drug Dictionary (WHODrug) and will be summarized by WHODrug standardized medication name and treatment group. Prior (medications with end dates prior to the randomization date) and concomitant medications will be listed.

### **3.2.5. Medical and Surgical History**

A listing of reported medical and surgical history will be provided by treatment group.

## **3.3. Analysis of Pharmacokinetic, Pharmacodynamic and Immunogenicity Endpoints**

See Section [2.9.3](#).

## **3.4. Analysis of Safety Endpoints**

Safety endpoints will be summarized separately for the blinded treatment period and the open-label treatment period.

### **3.4.1. Adverse Events**

Treatment-emergent adverse events (TEAEs) are defined as follows:

- During the blinded treatment period, an AE is treatment-emergent if it occurs or worsens in severity from pre-treatment after the first dose of study drug but before the first dose of narsoplimab in the open-label treatment period (blinded TEAE)
- During the open-label treatment period, an AE is treatment-emergent if it occurs or worsens in severity from the end of the blinded treatment period after the first dose of narsoplimab in the open-label treatment period (open-label TEAE)

All AEs will be classified by system organ class and preferred term using the Medical Dictionary for Regulatory Activities (MedDRA). An AE is considered treatment-related if the relationship to study drug is either probable or possible as assessed by the investigator.

Patient incidence by treatment group of the following AEs will be provided:

- Pre-treatment AEs (AEs that occurred prior to the start of study drug) by MedDRA system organ class (SOC), preferred term, and treatment group
- Blinded treatment period:

- TEAEs by MedDRA SOC, preferred term, and treatment group
- TEAEs by MedDRA preferred term and treatment group
- TEAEs that are treatment-related by MedDRA SOC, preferred term, and treatment group
- TEAEs by MedDRA preferred term, maximum severity, and treatment group
- TEAEs leading to study discontinuation by MedDRA SOC, preferred term, and treatment group
- TEAEs that are serious by MedDRA SOC, preferred term, and treatment group
- TEAEs that are treatment-related and serious by MedDRA SOC, preferred term, and treatment group
- TEAEs leading to death by MedDRA SOC, preferred term, and treatment group
- Open-label treatment period:
  - Open-label TEAEs by MedDRA SOC, preferred term, and treatment group
  - Open-label TEAEs by MedDRA preferred term and treatment group
  - Open-label TEAEs that are treatment-related by MedDRA SOC, preferred term, and treatment group
  - Open-label TEAEs by MedDRA preferred term, maximum severity, and treatment group
  - Open-label TEAEs leading to study discontinuation by MedDRA SOC, preferred term, and treatment group
  - Open-label TEAEs that are serious by MedDRA SOC, preferred term, and treatment group
  - Open-label TEAEs that are treatment-related and serious by MedDRA SOC, preferred term, and treatment group
  - Open-label TEAEs leading to death by MedDRA SOC, preferred term, and treatment group
- Blinded and open-label treatment periods combined for patients who receive narsoplimab only. TEAEs are determined relative to the first dose of narsoplimab
  - TEAEs by MedDRA SOC and preferred term
  - TEAEs by MedDRA preferred term
  - TEAEs that are treatment related by MedDRA SOC and preferred term
  - TEAEs by MedDRA preferred term and maximum severity
  - TEAEs leading to study discontinuation by MedDRA SOC and preferred term
  - TEAEs that are serious by MedDRA SOC and preferred term

- TEAEs that are treatment-related and serious by MedDRA SOC and preferred term
- TEAEs leading to death by MedDRA SOC and preferred term

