8.1. Patient Inclusion Criteria

Patients may be included in the study only if they meet all the following criteria during the Screening Period and Run-In Period:

1. Age 18 years or older at the onset of Screening
2. Understand and voluntarily sign an informed consent form in accordance with regulations and governing institutional review board (IRB) or independent ethics committee (IEC) requirements prior to any procedures or evaluations performed specifically for the sole purpose of the study
3. Biopsy-confirmed diagnosis of IgAN within 8 years prior to Screening or Run-In Visit 1
4. Documented history of proteinuria > 1 g/day within 6 months prior to Screening, or uPCR > 0.75 by spot urine, at Screening
5. Mean of two proteinuria measurements > 1 g/day at baseline

CONFIDENTIAL

No use, disclosure, or reproduction outside of Omertos without prior written authorization

6. Estimated glomerular filtration rate of ≥ 30 mL/min/1.73 m² calculated according to the Chronic Kidney Disease Epidemiology Collaboration (CKD-EPI) equation [[Levey 2009](#)] at Screening and baseline
7. Females should either a) not be of childbearing potential (i.e., surgically sterilized or postmenopausal for > 1 year), b) have a negative pregnancy test at Screening and baseline and, irrespective of sexual activity, must agree to use two medically reliable forms of contraception from study entry, throughout the study, and for at least 12 weeks after the last dose of study drug, including possible retreatments, or c) have a medically sterilized male partner. Acceptable methods of contraception include a reliable intrauterine device, hormonal contraception, a barrier method, or complete abstinence (periodic abstinence [e.g., calendar, ovulation, symptothermal, post-ovulation methods] and withdrawal are not acceptable methods of contraception).

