12. ASSESSMENT OF SAFETY

The Investigator and clinical facility staff are responsible for detection, recording, and reporting of events that meet the criteria and definition of Adverse Events as listed below. Adverse events will be recorded from time of signed informed consent through the last study visit. Serious Adverse Events will be recorded from time of signed informed consent through 30 days post last study visit. In addition, the Investigator and clinical facility staff are responsible for detection, recording, and reporting of pregnancies of study participants and of participants' partners as well as appropriate follow-up.

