14.1.12.2. Adverse Events

The incidence of all reported AEs and treatment-related AEs before the initiation of the open-label treatment of narsoplimab will be tabulated by treatment group. AE data collected during the

CONFIDENTIAL

No use, disclosure, or reproduction outside of Omeros without prior written authorization

open-label period will be summarized separately. AEs will be classified by System Organ Class (SOC) and Preferred Term (PT) using the Medical Dictionary for Regulatory Activities (MedDRA).

The focus of AE summarization for this study will be on treatment-emergent AEs (TEAEs). A TEAE is defined as an event that first occurs or worsens in severity after the first dose of study drug.

AEs will be listed and summarized by treatment group, MedDRA PT, severity, and relationship to study drug. In the event of multiple occurrences of the same AE with the same PT in one patient, the AE will be counted once as the worst occurrence. The incidence of AEs will be tabulated by SOC and treatment group. AEs leading to premature discontinuation of study drug or withdrawal from the study will be summarized and listed in the same manner.

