### 1.2. Study Design

This is a Phase 3, double-blind, randomized, placebo-controlled study in patients aged 18 years and above with a biopsy-confirmed diagnosis of IgAN and with 24-hour UPE  $> 1$  g/day at baseline. During the study, all patients will continue optimized renin angiotensin system blockade. The study consists of 5 periods: Screening, Run-In, Initial Treatment (Weeks 1-12), Response Evaluation (Weeks 13-36), and Follow-Up (Weeks 37 to Week 96/end-of-study). The duration of study for each patient is expected to be approximately 112 weeks.

Eligible patients will be randomized equally to one of the study treatments (placebo or narsoplimab 370 mg). Randomization will be stratified by the baseline eGFR level ( $\geq 30$  to  $\leq 45$  mL/min/1.73 m^2 and  $> 45$  mL/min/1.73 m^2) and by baseline 24-hour UPE ( $> 1$  to  $< 2$  g/day and  $\geq 2$  g/day). All randomized patients are to receive 12 weekly doses of initial study treatment. Following treatment completion, the proteinuria response will be evaluated at several timepoints, and additional study treatment will be given to patients as specified in Section 7.1 of the protocol.

Patients with baseline 24-hour UPE  $> 2$  g/day will be allowed to receive 12-weeks of open-label active drug (narsoplimab) on or after Week 72 (18 months post randomization) as stated in the protocol, provided that they meet the conditions stipulated below:

- Patient has < 30% decrease in 24-hour UPE from baseline, and
- Proteinuria is  $\geq 3.0$  g/day at any time on or after 72 weeks from randomization, as confirmed by 2 24-hour UPE measurements at least 2 weeks apart, and
- Patient has worsening renal function, defined as a decline in eGFR of  $> 5$  mL/min/1.73 m^2 from baseline

Patients who receive treatment with open-label narsoplimab should continue to attend all study visits and complete all required study procedures. Neither the Investigator nor the patient who receives open-label treatment will be unblinded to the patient's original treatment assignment.

The primary efficacy endpoint of this study is the change from baseline in log-transformed 24-hour UPE in g/day at 36 weeks from baseline in patients in the high-risk proteinuria group (24-hour UPE  $\geq 2$  g/day). A sample size of 180 patients is planned for the primary endpoint.

The key secondary efficacy endpoints of this study are:

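### The blinded TEAE window has no close tied to the last blinded dose, so the only planned comparison is crude incidence over follow-up that may be mostly off drug

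*SAP*

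**What the plan says.** SAP 3.4.1 defines a blinded TEAE as an event that occurs or worsens "after the first dose of study drug but before the first dose of narsoplimab in the open-label treatment period (blinded TEAE"). Protocol 14.1.12.2 gives a start and no end: "A TEAE is defined as an event that first occurs or worsens in severity after the first dose of study drug". Protocol 12.2.1 does the same. For patients who never receive open-label drug, the practical end comes from Protocol Section 12: "Adverse events will be recorded from time of signed informed consent through the last study visit". Serious events are recorded for a further 30 days.

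The only split by period is in SAP 3.4: "Safety endpoints will be summarized separately for the blinded treatment period and the open-label treatment period". The measure is stated in SAP 3.4.1: "Patient incidence by treatment group of the following AEs will be provided". The listed tables include no patient-years, exposure-adjusted rate or on-treatment subset. The combined blinded and open-label table for narsoplimab recipients also has only a start.

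Dosing is intermittent. SAP 1.2 says: "All randomized patients are to receive 12 weekly doses of initial study treatment". Protocol 7.1 adds 6 weeks if 24-hour UPE exceeds 1 g at Week 12, one 6-week relapse course in the Response Evaluation Period and one 12-week relapse course in the Follow-Up Period. Blinded dosing therefore totals 12 to 36 weeks in a 96-week study. SAP 3.2.2.2 bounds each blinded treatment period by its first and last dose, but only for exposure. SAP 3.4.1 uses the term blinded treatment period without saying where it ends.

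**The concern.** A patient whose twelfth and last dose falls on Day 78 and who has an event on Day 650 is 572 days, about 82 weeks, past dosing. That event still counts as treatment-emergent, alongside events in the first weeks of dosing. If the drug raises a risk only while it is acting, background events from the off-drug months enter both arms and pull the incidence ratio towards 1.

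Infection is where this matters most. Protocol 5.3.1 discusses infection at length as the potential target-related risk, and Protocol 5.3.3 commits to close monitoring for it. The planned between-arm tables cannot distinguish no excess from an excess confined to dosing and diluted by follow-up.

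**Working it through.** The documents give no event rate, ratio or off-drug share, so there is no figure of the plan's own to reproduce. The time base is consistent: 4 weeks of screening + 12 of run-in + 96 = 112 weeks, as stated.

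**Inputs**
- SAP Table 2 target days: dose 12 = Day 78; Week 24 = 162; Week 36 = 246; Week 48 = 330; Week 72 = 498; Week 96 = 666.
- Protocol 10.2.4: six weekly extended doses, the first no later than 14 days after T12. The last dose is Day 85 + 35 = 120 with a 7-day gap, or Day 92 + 35 = 127 with a 14-day gap.
- Protocol Table 1: one 6-week and one 12-week relapse course. Assumption: each starts 14 days after the assessment day.
- An 84-day tail. The only such interval in the documents is in Protocol 8.1, "for at least 12 weeks after the last dose of study drug, including possible retreatments", which is a contraception rule.

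**Step 1: share of the window more than 12 weeks off drug.** Share = 1 - (days in a course or within 84 days of its last dose)/666.

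| Blinded courses | Days covered | Share off drug |
|---|---|---|
| 12 doses | 78 + 84 = 162 | 75.7% |
| 18 doses, 7-day gap | 120 + 84 = 204 | 69.4% |
| 18 doses, 14-day gap | 127 + 84 = 211 | 68.3% |
| 12 doses + 6 weeks after Week 24 | 162 + 120 = 282 | 57.7% |
| 18 doses + 6 weeks after Week 24 | 295 (overlapping) | 55.7% |
| 12 doses + 12 weeks after Week 72 | 162 + 155 = 317 | 52.4% |
| 18 doses + 12 weeks after Week 48 | 204 + 162 = 366 | 45.0% |
| All courses, relapse at Weeks 24 and 72 | 295 + 155 = 450 | 32.4% |
| All courses, relapse at Weeks 36 and 72 | 204 + 120 + 155 = 479 | 28.1% |

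Rows with retreatment after 18 doses use the 7-day gap. The average depends on an unknown relapse rate. If 40% of 18-dose patients had every course (31.4% off drug with relapse at Weeks 24 and 48), it would be 0.6 x 69.4 + 0.4 x 31.4 = 54%.

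**Step 2: illustrative dilution, no retreatment.** Assume a constant background rate r, doubled from the first dose to 12 weeks after the last. Whole study T = 96/52.18 = 1.840 years. Window o = 23.1/52.18 = 0.443 years (162 days) or 30.1/52.18 = 0.577 years (211 days).
- Over 96 weeks: [1 - exp(-r(T + o))] / [1 - exp(-rT)]
- Inside the window: [1 - exp(-2ro)] / [1 - exp(-ro)]

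For r = 0.2 and o = 0.443 these are 0.3665/0.3079 = 1.19 and 0.1623/0.0847 = 1.92.

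| r per year | Ratio over 96 weeks | Ratio inside the window |
|---|---|---|
| 0.2 | 1.19-1.25 | 1.89-1.92 |
| 0.5 | 1.13-1.17 | 1.75-1.80 |
| 1.0 | 1.07-1.08 | 1.56-1.64 |

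**Step 3: how far this carries.**
- With retreatment such that half of follow-up is in the window (o = 0.920) and r = 0.2, the ratios are 0.424/0.308 = 1.38 overall and 1.83 inside. Dilution is smaller but still present.
- For a patient cut off at Week 36 (Day 246), the off-drug share is (246 - 162)/246 = 34% after 12 doses or (246 - 204)/246 = 17% after 18. The Week 96 figures do not describe the interim data.

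**The case against.** The all-follow-up table has a real merit: it compares randomized arms over the same calendar span. An on-treatment table does not. Extended dosing depends on Week 12 UPE and retreatment requires a prior 30% response, so on-treatment time is selected by response and may differ by arm. Patient-years correct for unequal length, not for selection. This stands, and it is why the on-treatment table should be supportive and paired with a fixed-calendar one.

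The size rests on assumptions. The doubling, the background rates and the 12-week tail are not in the documents. A constant hazard also ignores ascertainment: visits are weekly during dosing, but after Week 48 contacts are 12 weeks apart. If off-window capture were halved, the 96-week ratios would be 1.17-1.40 rather than 1.07-1.25. For rare events the separate table gains little: at 0.02 per year with 225 per arm, the window holds about 2-3 placebo events against 4-5 on drug.

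A reader might go on to compare the power to detect the doubled risk over the two spans. That would describe a test nobody plans, because SAP 2.9.4 makes all safety analyses descriptive.

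There are partial safeguards: investigator-related TEAEs by arm, laboratory results and vital signs by visit, exposure by blinded period, recorded onset dates and IDMC review. None gives a between-arm adverse event comparison by proximity to dosing.

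**Conclusion.** The gap is real and cheap to close. The blinded TEAE window has no end tied to the last blinded dose, and only crude incidence over the whole window is planned. For never-retreated patients followed to Week 96, 68-76% of it is more than 12 weeks off drug; for retreated patients, about 28-58%. Under the stated assumptions a doubled risk shows as about 1.07-1.25 without retreatment, against 1.56-1.92 inside the window.

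Three stronger readings are not supported. A reader might infer that the window never closes, but it does, at the first open-label dose or the last study visit. A reader might apply a figure of about 70% to the whole trial, but that omits blinded retreatment, whose frequency is not given. A reader might conclude that the plan conceals a known harm, but the documents report no such excess and Protocol 5.3.3 judges the infection risk low. The planned table is not wrong; on its own it is a weak instrument for an on-drug risk.

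**What to change.** In SAP 3.4.1, state where the blinded treatment period ends for adverse events and reconcile this with SAP 3.2.2.2. Keep the all-follow-up TEAE table and add two sets:

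- **(a) On- and off-treatment.** Blinded TEAE, serious TEAE and infection tables, split into on-treatment events (first dose of each blinded course to a pre-specified interval after its last dose) and off-treatment events. Give patient-years and exposure-adjusted rates for each. The sponsor should justify the interval, for example from PK/PD. Twelve weeks is one candidate, but in the documents it serves contraception only.
- **(b) Fixed calendar.** The same event tables from first dose to a common early time point such as Week 24 or Week 36, so that the arms are compared over a span that does not depend on response.

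The cost is SAP wording, one flag derived from dates already collected, and more tables with fewer events in each. Set (a) should be labelled supportive because its person-time is response-selected. Trial conduct, dosing and alpha are unaffected.
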